#### Randomization Method and Blinding

11.4. Describe the randomization method and blinding (if applicable).

Among interested Seattle area primary care practices and 21 Group Health primary care clinics in 5 western Washington counties (King, Snohomish, Pierce, Thurston, and Kitsap), we will pair clinics based upon the number of vaccines doses ordered in the prior year and subsequently enroll and randomize up to 30 to the control and SPARCK intervention arms. We will conceal study arm allocation and describe the study generally as one that seeks to determine the impact of soliciting parent attitudes regarding preventive care topics before health supervision visits on improved health outcomes.

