## 12. Study Population

#### 12.1. Describe inclusion criteria.

Parents: Parents must be English speaking, ≥18 years old, have a newborn singleton infant ≤2 months, born at ≥35 weeks gestation who is receiving pediatric care at an enrolled Seattle area clinic or Group Health clinic, and be vaccine hesitant (defined as ≥2 positive responses on questions 1, 3, 6 and 8 on the eligibility screening survey (Appendices F and P); these questions constitute the PACV-SF).

Newborns: Newborns 0 - 2 months old whose parents enroll in the study will be included.

Providers: All Seattle area primary care practices and Group Health primary care clinics within a 5 county region in western Washington (Snohomish, King, Pierce, Thurston, and Kitsap Counties) will be eligible to participate. Once clinic leadership has agreed to participate, all pediatric and family practice providers (MD, DO, ARNP, PA-C) at those clinics will be eligible to participate.

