#### 13. Study Procedures

This section should list the procedures, observations, measures, etc. at each study visit, including history, examination, study drug administration or other interventions (can be provided in table form as a Table of Evaluations often used in protocols).

13.1. **Describe study visits.** Parents will be approached and screened for this study by a research assistant (RA) over the telephone (Group Health parents only) or at their child's clinic upon check-in for their child's health supervision visit that occurs at or before 2 months of age. For Group Health parents who are screened over the telephone, an RA will meet the parent at their child's 2 month health supervision visit to complete the consent and enrollment process. This enrollment encounter will include having the parents who are eligible and agree to participate complete the demographic survey (Appendix G). If enrollment occurs at a health supervision visit prior to 2 months of age, an RA will meet the parent back at their child's clinic at the time of their child's 2 month health supervision visits to have them complete an electronic version of the study survey using an iPad® (i.e. the intervention survey at SPARCK clinics (Appendix A) and the placebo survey at control clinics (Appendix B)). If enrollment occurs at the 2 month health supervision visit, the RA

Study Title: Screening Parents about Recommended

Care for Kids (SPARCK) Study

Principal Investigator: [name], MPH

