**Version Date: 5/1/2018** 

will simply proceed to administer the intervention or placebo survey right after enrollment. The RA will generate and print an automated summary sheet of the parent's screening results, and hand the printed summary sheet to the child's provider before the visit begins (Appendices C and D). They will also alert the provider that their patient is a SPARCK study participant by writing, "SPARCK STUDY" in the scheduling notes section of the child's electronic health record. This process will be repeated before the child's 6 month health supervision visit. After their child's 6 month health supervision visit, parents will complete a survey about their satisfaction with their child's provider at the clinic (Appendix E).

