#### **Analysis Plan and Statistical Methods**

16.1. Outline the data analysis plans relating to each specific aim/objective or research hypothesis mentioned in section 11 above. It should be clear how the analysis results will allow each aim/objective to be answered. The analysis plans for the primary aim should be detailed. Analysis plans for secondary aims may be brief, but must be included. Give the names of specific statistical methods and state which variables will be used with them.

Aim1: To evaluate the effectiveness of the SPARCK intervention in increasing vaccine acceptance. We will conduct an intention-to-treat analysis for Aim 1. Parents will be the unit of analysis. We will examine baseline characteristics among control and SPARCK parents using Pearson's  $\chi 2$  tests (or Fisher's exact tests) for categorical variables and t-tests for continuous variables to assess for any unbalanced confounders between control and SPARCK arms. To compare our primary outcome of percent days underimmunized between control and SPARCK arms, we will apply linear mixed effects regression modeling to the percent days under-immunized with clinic-specific random-effects to account for within-clinic correlation. If unbalanced confounders are detected between arms, they will be adjusted for in the mixed effects models.

Aim 2: To assess how parent-rated experience of the vaccine discussion changes as a function of the SPARCK intervention. For Aim 2, we will use Pearson's χ2 test to compare parent (binary) ratings of their vaccine discussion between control and SPARCK

Study Title: Screening Parents about Recommended

Care for Kids (SPARCK) Study

Principal Investigator: [name], MPH

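### Baseline significance tests choose the covariates in the Aim 1 model; a short list fixed in advance would settle the primary estimate at little cost and may add some precision

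*Combined protocol and SAP*

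**What the plan says.** Section 16.1 (Aim 1) states "Parents will be the unit of analysis" and compares baseline characteristics by arm with Pearson chi-square or Fisher tests for categorical variables and t-tests for continuous ones. The rule that follows is "If unbalanced confounders are detected between arms, they will be adjusted for in the mixed effects models". The outcome model is a linear mixed model "with clinic-specific random-effects to account for within-clinic correlation"; no such allowance is described for the baseline tests. The plan gives no list of candidate covariates and no p-value at which imbalance counts as detected. The form's own instruction at the head of section 16.1 reads "Give the names of specific statistical methods and state which variables will be used with them". Aim 2 carries a similar trigger for parent factors; this point concerns Aim 1.

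The trial already holds possible prognostic variables in both arms. Section 12.1 defines hesitancy as two or more "positive responses on questions 1, 3, 6 and 8 on the eligibility screening survey", so the PACV-SF is known for every enrolled parent. Section 11.4 says "we will pair clinics based upon the number of vaccines doses ordered in the prior year", so that figure is known for every paired clinic, yet it does not appear in the section 16.1 model.

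**The concern.** A test between arms selects a variable by the size of its chance difference, not by its relation to under-immunization. A strong predictor that balances well is omitted, and the precision it could have given is lost. The model that yields the primary estimate is also unknown until someone has compared the arms and judged which differences count, with no written threshold to guide that judgement. At stake are a fixed primary estimate and, if the available covariates predict the outcome, some power. Power is expensive to buy with numbers here: section 16.2 expects about 3500 parents to be screened to enrol 160.

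**Working it through.** **Inputs from section 16.2.** SD 33.3; 80 parents per arm; 16 clinics of 10; alpha 0.05 (taken as two-sided); outcome ICC 0.02, so the design effect is 1 + 9 × 0.02 = 1.18. The target is 30 days per vaccine from birth to 8 months. Taking 8 months as 243 days (an assumption), 30/243 = 12.35 percentage points.

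**The plan's own figure.** SE = 33.3 × √(2 × 1.18/80) = 5.72. The normal approximation gives 12.35/5.72 − 1.96 = 0.20, or about 58% power; the noncentral t with 14 df gives 52%. The stated 90% is not reproduced under this conversion. It would need a difference of about 20.0 points on 14 df. That is a separate matter and does not affect the shares below.

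**Share of the variance reduction lost.** Let Z be the covariate's arm difference divided by its true standard error. Fixed adjustment always removes the part of the error due to Z. Test-then-adjust removes it only when |Z| > c, where c = z(1−a/2)/√(1 + 9 × ICCx), a is the test threshold and ICCx is the covariate's ICC. The denominator appears because the tests treat parents as independent. The share kept is 2[c·φ(c) + 1 − Φ(c)]. For a = 0.05 and ICCx = 0.02, c = 1.960/√1.18 = 1.804, and the share kept is 2(1.804 × 0.0783 + 0.0356) = 0.354, a loss of 65%. The covariate is flagged 7.1% of the time. Share lost:

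| Threshold | ICCx 0 | 0.02 | 0.05 | 0.10 |
|---|---|---|---|---|
| 0.05 | 72% | 65% | 55% | 43% |
| 0.10 | 56% | 49% | 40% | 30% |
| 0.20 | 35% | 29% | 23% | 17% |

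Reading across a row, the loss falls as clustering grows, because a test that ignores clustering flags more often. The loss comes from selecting by significance.

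**Simulation check** (threshold 0.05, ICCx 0.02). A clinic-level analysis with 10,000 replicates kept 36% to 40%. A random-intercept REML model with four covariates and 3,000 replicates lost 67% to 73% for R² of 0.3 down to 0.1. The REML results are noisier: at ICCx 0 they gave 82% against 72% from the formula. Type I error was 0.044 to 0.055 in the first and about 0.025 to 0.042 in the second.

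**Absolute gain from fixed adjustment.** SE = 33.3 × √(2 × 1.18 × (1 − r²)/80), with noncentral t on 14 df unadjusted and 13 df adjusted (one clinic-level df for the pairing variable). The documents give no covariate-outcome correlation r, so it is assumed. Equivalent N is 160/(1 − r²).

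| r | SE | Power at 12.35 points | Equivalent N |
|---|---|---|---|
| 0 (unadjusted) | 5.72 | 52.0% | 160 |
| 0.1 | 5.69 | 52.0% | 162 |
| 0.2 | 5.60 | 53% | 167 |
| 0.3 | 5.46 | 55% | 176 |
| 0.4 | 5.24 | 59% | 190 |
| 0.5 | 4.95 | 64% | 213 |

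At about 20.0 points, where unadjusted power is 90%, r = 0.2 to 0.5 gives 91%, 92%, 94% and 96%. With 30 clinics (design effect 1.087), power at 12.35 points is 58% unadjusted and 60%, 62%, 66% and 71%. In the clinic-level simulation, test-then-adjust added only 0.1 to 1.2 points of power over no adjustment, because the reported standard error shrinks only when a variable happens to be flagged.

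**The case against.** The strongest reply is that the benefit may be close to nothing. Every enrolled parent is already hesitant and PACV-SF positives can only be 2, 3 or 4, which limits what that score can explain. No document shows that doses ordered predict the outcome. At r = 0.1 the lost degree of freedom cancels the gain. This stands, and it is why the case rests first on fixing the estimate and only second on power.

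The trigger also has a rationale. Parents enrol after clinics are randomised, so recruitment could differ by arm and produce real imbalance. That stands as a reason to keep a demographics-adjusted analysis, but not as a reason to let tests choose the variables in the primary one.

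The loss formula describes parent-level covariates. It does not describe doses ordered, which is a clinic-level variable whose imbalance the pairing constrains. The power table rests on a clinic-level t approximation, not on the mixed model itself.

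A reader might infer that the plan throws away two thirds of the available precision. The documents do not support that as a property of the plan: they state neither a threshold nor a covariate ICC, and the 0.02 in section 16.2 is a sample-size assumption for the outcome. A reader might also infer that ignoring clustering causes the loss; the calculation shows that it lessens it.

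**Conclusion.** The concern holds as a cheap improvement. As written, the covariates of the Aim 1 model depend on tests with no stated threshold, so the primary estimate is not pre-specified, and prognostic variables that balance are left out. That part needs no assumption. The size does: the loss for a parent-level covariate is about 65% at threshold 0.05 and covariate ICC 0.02, and 72% to 17% over the assumed grid. It is a share of an unknown total, worth between nothing and about 12 points of power for r between 0.1 and 0.5 at 16 clinics and 12.35 points. It would be wrong to read this as a false-positive problem, since type I error was not inflated in simulation. Nor does the rule explain the gap between 52% and the stated 90% power, which arises before any covariate is considered.

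**What to change.** Delete the test trigger and report baseline characteristics descriptively. Pre-specify the primary analysis as a linear mixed model with arm, PACV-SF score, prior-year vaccine doses ordered and a clinic random effect.

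- Add a hepatitis B birth-dose indicator only if the immunization records allow it to be derived in the same way in both arms. The documents do not say whether hospital doses are captured. Doses at or after the 2-month visit are not baseline, because in the SPARCK arm staff "hand the printed summary sheet to the child's provider before the visit begins".
- Do not adjust for the full PACV, which only the SPARCK arm completes (sections 11.1 and 11.3).
- State how missing covariate values are handled. Section 16.3 excludes missing data, and an incomplete covariate would otherwise remove families from the primary model. PACV-SF and doses ordered should be complete by design.
- Keep two sensitivity analyses: the unadjusted model, and a model adding demographic-survey variables named in advance.

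The cost is SAP wording and, if it is used, one derived variable. The downsides are one clinic-level degree of freedom (about 0.5 points of power at 16 clinics) and little or no gain if the covariates predict weakly. The PACV-SF is also asked after clinics are randomised, which is a further reason to keep the unadjusted model.

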**Version Date: 5/1/2018** 

#### **Investigator Help**

## 11. Investigational Plan

## 11.1. Describe the general schema of the study design.

Figure 1. Study Design

This study is a cluster randomized controlled trial. We will pair up to 30 Seattle area primary care clinics and Group Health primary care clinics based upon the number of vaccine doses ordered and enroll and randomize clinics to control and SPARCK arms. We will screen parents for vaccine hesitancy using the Parent Attitudes about Childhood Vaccines Short Form survey (PACV-SF) (Appendix F). Parents in the SPARCK arm of the study will take the intervention survey (which has the PACV embedded in it) to their child's 2 and 6 month visits (Appendix A) whereas parents in the control arm of the study will take a placebo survey about childhood health topics (Appendix B). The results of these surveys will be communicated to the child's provider (Appendices C and D). After the child's 6 month visit, parents in both arms will complete a satisfaction survey about their visit experience (Appendix E). When the child is 8 months of age, we will use an automated clinic immunization database to determine their immunization status. For participants who were lost to follow up (i.e. those who did not have a 6 month appointment, or those who did not have a 2 and 6 month appointment), we will also use Washington State Immunization information System records to determine participant immunization status.

Study Title: Screening Parents about Recommended

Care for Kids (SPARCK) Study

Principal Investigator: [name], MPH

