**Version Date: 5/1/2018** 

arms. We will apply mixed effects logistic regression model to this outcome to account for within-clinic correlation and any unbalanced parent confounding factors. When summarizing parent experience as a continuous variable, we will apply Box-Cox transformation if it is highly skewed and linear mixed effect models to examine the differences in parent experience between control and SPARCK arms.

Aim 3: To characterize the effect of the SPARCK intervention on provider perceptions of barriers to quality vaccine discussions. For Aim 3, providers will be the unit of analysis. We will compare the pre- and post-study proportions of control and SPARCK providers reporting that time, understanding of specific parental vaccine concerns, and knowledge of overall parental vaccine attitudes were significant barriers (defined as 4 or 5 on a 1-5 scale) to quality vaccine discussions. We will use t-tests for an unadjusted analysis of the pre-post differences between control and SPARCK arms and multivariate linear regression for adjusted analyses that control for potential confounding variables such as provider demographic and practice characteristics.

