## 16.2. Provide a justification for the sample size and power calculations.

Based on preliminary data, children of parents with a positive PACV-SF had a mean percentage of days under-immunized of 27.1% (standard deviation [SD] 33.3) from birth to 8 months of age for 4 vaccines combined (hepatitis B, DTaP, Hib, and IPV). To be able to detect with adequate power (90%) a decrease in under-immunization of 30 days per vaccine—a decrease that has the potential to be clinical meaningful since it equals the 1 month recommended interval a parent has before their child is considered late for a vaccination dose—we need to enroll 160 parent/newborn pairs total, with 80 per arm and 10 at each of the 16 study clinics (assuming an  $\alpha$  of 0.05 and an intraclass correlation coefficient for within-clinic correlation of 0.02).

In our original calculation, we assumed 80% of GH parents would be reached, a conservative estimate of a 20% prevalence of GH parents who will have a positive PACV-SF, 10% of VHPs who fail to meet other study eligibility requirements, 25% of VHPs who do not agree to participate (unpublished data), a 10% attrition rate over the course of the study, and 70% who remain continuous GH members, resulting in the need to approach 2400 parents to reach our sample size goal. From 2010 – 2012, there was an average of 2679 GH births per year in the 5 Washington State counties from which we will recruit parents. Reaching our sample size goal should therefore be feasible given our designated 15 month recruitment period. However, we now know that the vaccine hesitancy rate at GH is about 5%. Therefore, we need to screen approximately 3500 parents to reach the desired sample size goals of 160.

For Aim 2, we will have 80% power with a sample size of 160 parents to detect a 17% increase in the proportion of parents who rate their visit highly, assuming a baseline proportion of 72%.  For Aim 3, we will have 80% power to detect a 14% pre-post difference in the proportion of providers who perceive time as a barrier to quality vaccine discussions between control (1% pre-post difference) and SPARCK arms (15% pre-post difference), assuming a baseline proportion of 62% and 56 providers in each arm.

Study Title: Screening Parents about Recommended

Care for Kids (SPARCK) Study

Principal Investigator: [name], MPH

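### Aim 2 names two between-arm tests of the same binary rating, one of which ignores clinic randomisation, and does not say which decides

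*Combined protocol and SAP*

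**What the plan says.** Section 11.1 states the design: "This study is a cluster randomized controlled trial". Section 16.2 sets the size: "we need to enroll 160 parent/newborn pairs total, with 80 per arm and 10 at each of the 16 study clinics".

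For the binary version of the Aim 2 outcome, section 16.1 gives two consecutive sentences, separated only by a page break:

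- First: "we will use Pearson's χ2 test to compare parent (binary) ratings", with the comparison being between the control and SPARCK arms.
- Then: "We will apply mixed effects logistic regression model to this outcome to account for within-clinic correlation". The same sentence adds unbalanced parent confounders as a second purpose of the model.

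If parent experience is summarised as a continuous score, the plan uses "linear mixed effect models to examine the differences in parent experience between control and SPARCK arms", with no unclustered test beside them. Neither the chi-square nor the logistic model is labelled as the test that decides Aim 2.

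**The concern.** A Pearson chi-square on individual parents takes all 160 ratings as independent. Parents at one clinic share providers and procedures, and the whole clinic is in one arm, so any positive within-clinic correlation makes the chi-square p-value too small. Following the plan as written therefore produces one p-value for Aim 2 that is not valid for the design, alongside one that allows for clustering. If the two fall on opposite sides of 0.05, the plan has no rule for which one is the answer.

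Two features make the chi-square more than a descriptive habit. Its stated purpose is to compare the arms on an outcome, whereas Aim 1 reserves chi-square and t-tests for baseline characteristics and takes its outcome straight to a model with clinic random effects. And the Aim 2 power statement in 16.2 matches an unclustered comparison, as shown in the working.

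**Working it through.** **Inputs**

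- 80 parents per arm, 16 clinics of 10 (16.2), so 8 clinics per arm.
- Baseline proportion 72%, increase of 17 points to 89%, stated power 80% (16.2, Aim 2).
- α = 0.05 and ICC = 0.02, both stated in 16.2 for Aim 1. Applying them to the parent rating, and taking the test as two-sided, are assumptions.

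**Step 1. The plan's own Aim 2 power.** With no allowance for clustering and unpooled variance:

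- SE = √[(0.72×0.28 + 0.89×0.11)/80] = √(0.2995/80) = 0.0612
- Power = Φ(0.17/0.0612 − 1.96) = Φ(0.82) = 79.3%

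The arcsine formula also gives 79.3%, and the pooled-variance formula gives 78.0%. So the stated 80% reproduces approximately, but only without a design effect. With 10 parents per clinic and ICC 0.02, the design effect is 1 + (10 − 1)×0.02 = 1.18. The effective number per arm is then 80/1.18 = 67.8, and power falls to 72.5% (unpooled) or 70.9% (pooled).

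**Step 2. False-positive rate of the chi-square.** Let DE = 1 + (m − 1)×ICC, with m parents per clinic. Under the null, the chi-square's z statistic has variance of about DE instead of 1, so the actual two-sided rate is 2×[1 − Φ(1.96/√DE)].

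For m = 10 and ICC 0.02: 1.96/√1.18 = 1.804, and 2×[1 − Φ(1.804)] = 7.1%.

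The simulation column uses beta-binomial data with 8 clinics of 10 per arm, a true proportion of 72% in both arms and 200,000 replicates.

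| ICC | DE | Formula | Simulation |
|---|---|---|---|
| 0 | 1.00 | 5.0% | 5.2% |
| 0.01 | 1.09 | 6.05% | 6.1% |
| 0.02 | 1.18 | 7.1% | 7.4% |
| 0.05 | 1.45 | 10.4% | 10.7% |
| 0.10 | 1.90 | 15.5% | 16.0% |

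In the same simulation a t-test on clinic proportions held 4.9% to 5.1% throughout, so the excess comes from ignoring the clinics.

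**Step 3. Sensitivity to cluster size at ICC 0.02.** With the 10% attrition in 16.2 there are 9 parents per clinic, DE is 1.16 and the rate is 6.9%. If the 160 parents were spread over the maximum of 30 clinics in 11.1, there are 160/30 = 5.3 per clinic, DE is 1.087 and the rate is 6.0%.

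**Step 4. The planned mixed model.** A smaller simulation of 1,500 null trials fitted a logistic model with a clinic random intercept and used a likelihood-ratio test. It rejected 5.1% at ICC 0.02 and 6.5% at ICC 0.05, against 7.1% and 10.3% for the chi-square in the same trials. The Monte Carlo standard error near 5% is √(0.05×0.95/1500) = 0.6 points. The model is therefore close to nominal at ICC 0.02. With 16 clinics it is not exact at larger correlations, but it is much nearer to 5% than the chi-square.

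**The case against.** The strongest reply is that the plan already handles clustering. The sentence after the chi-square applies a mixed logistic model to the same outcome, for that stated purpose. A simple comparison followed by a model is also a pattern in the section: Aim 3 labels its t-tests as unadjusted and its regression as adjusted. Aim 2 is a secondary objective (9.2), and the form allows brief plans for secondary aims.

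Most of this stands. A reader might infer from the chi-square sentence that the Aim 2 analysis as a whole ignores the design and runs above 5%. The documents do not support that: a model that accounts for clinics is specified, and nothing says that the chi-square decides. Nor do they support an expectation that the more favourable p-value would be chosen. The power figure fits an unclustered test, but that does not prove the chi-square is the intended deciding test.

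Two things remain. Calling the chi-square the unadjusted analysis would not make its p-value valid, because clustering comes from the randomisation and is not an optional covariate. And the same form asks that it be clear how the results will answer each aim, which two unranked tests of one hypothesis do not achieve.

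**Conclusion.** Wrong as written, and minor. Section 16.1 names an individual-level between-arm test that is not valid for inference in a clinic-randomised trial, beside a model that is appropriate, and gives no rule between them.

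The size is conditional. The rate of about 7.1% applies only to the chi-square p-value, and only if the Aim 1 ICC carries over to the parent rating, with 10 parents per clinic and a two-sided 5% level. Since the plan gives no ICC for this outcome, the range in the working should be read with it; at an ICC of 0 there is no inflation. It is not the false-positive rate of the Aim 2 plan, because inference from the mixed model is not subject to it.

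**What to change.** In 16.1, under Aim 2:

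- Delete the chi-square as an inferential comparison between arms.
- State that Aim 2 inference for the binary rating rests on the already planned mixed-effects logistic model with a clinic random intercept.
- Report the raw percentages by arm descriptively, without a chi-square p-value.

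Whether the version of that model with or without confounders leads is a matter of preference, and this point does not depend on it.

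The cost is one sentence. No new data, method or sample size is needed.
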